5.2 Patient Evaluation Flowsheet: Pre-Treatment, On-Study, and after Protocol Treatment
 For Patients Randomized to Durvalumab and Tremelimumab (Arm 2)

| Required Investigations | PRE-STUDY (≤14 days prior to randomization, unless otherwise indicated) | DURING Protocol Treatment Day 1 each cycle, and as clinically indicated (unless otherwise indicated) | AFTER Protocol Treatment is Permanently Discontinued ¹ | | | |
|---|--|---|---|--------------------------|---|---------------------------|
| | | | PRIOR to objective disease progression | | AFTER objective disease progression | |
| | | | 4 weeks after end of last cycle date | Every 4 weeks thereafter | 4 weeks after end of last cycle date ¹ | Every 12 weeks thereafter |
| History and Physical Exam² | | | | | | |
| Including: height (baseline only), weight, ECOG performance status, clinical tumour measurements (if applicable) | X | X | X | X | X | |
| Vital Signs (blood pressure, heart rate, temperature) | X | X ³ | | | | |
| Concomitant Medications | X | X | X | | X | |
| Overall Survival | | | | | | |
| Survival status assessment | | X | X | X | X | X ⁴ |
| Hematology^{2,5} | | | | | | |
| CBC, differential (including lymphocytes), platelets | X | X ² | X | X | X | X ⁵ |
| Coagulation^{2,5} | | | | | | |
| PTT, PT/INR | X | X ² | X | X | X | X ⁵ |
| Biochemistry^{2,5} | | | | | | |
| Serum Creatinine, Chloride, Sodium, Potassium, Calcium, Magnesium, Bilirubin, ALP, AST and ALT, LDH, Albumin, TSH ⁶ , Amylase, Lipase, Serum CEA | X | X ² | X | X | X | X ⁵ |
| Creatinine Clearance (calculated) | X | as clinically indicated | | | | |
| Glucose | X | as clinically indicated | | | | |
| Radiology⁷ | | | | | | |
| Chest/abdomen/pelvis CT or MRI scan | X ≤ 28 days | X ⁷ Every 8 weeks from randomization until objective disease progression (maintain schedule even if cycles are delayed) | | | | |
| Other scans as necessary to document all measurable and non-measurable disease | X ≤ 28 days | | | | | |
| Other Investigations | | | | | | |
| Pregnancy Test ⁸ | X | | | | | |
| ECG | X | as clinically indicated | | | | |
| Dipstick Urinalysis (including protein, specific gravity, glucose and blood) | X | | | | | |

table continued on next page ...

ADMIN UPDATE #1: 2018-JAN-24

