| Required Investigations | PRE-STUDY (≤14 days prior to randomization, unless otherwise indicated) | DURING Protocol Treatment Day 1 each cycle, and as clinically indicated (unless otherwise indicated) | AFTER Protocol Treatment is Permanently Discontinued ¹ | | | |
|--|--|---|---|--------------------------|---|---------------------------|
| | | | PRIOR to objective disease progression | | AFTER objective disease progression | |
| | | | 4 weeks after end of last cycle date | Every 4 weeks thereafter | 4 weeks after end of last cycle date ¹ | Every 12 weeks thereafter |
| Correlative Studies | | | | | | |
| Archival Tissue Sample ⁹ (mandatory) | Availability of sufficient tissue must be confirmed prior to randomization | Submit tissue within 4 weeks of randomization | | | | |
| Whole blood, plasma and serum ⁹ (mandatory) | After randomization but before first dose of study treatment | To be done at 8 weeks and at the time of objective disease progression ¹⁰ , if not already done | | | | |
| Adverse Events | | | | | | |
| Adverse Event Assessment ¹¹ | X (To document residual adverse events from previous therapy and baseline symptoms) | X ¹² (To be evaluated continuously for adverse events) | X | X ¹³ | X ¹ | X ¹³ |
| Quality of Life | | | | | | |
| EORTC QLQ C30 ¹⁴ | X | At 4, 8, 12, 16 and 24 weeks after randomization, then every 12 weeks thereafter (until deterioration to ECOG PS 4 or hospitalization for end of life care) | | | | |

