| 
 All patients will be seen at 4 weeks after the end of the last cycle date. Thereafter, continued follow-up is not required for patients who go off protocol treatment with unequivocal progressive disease, except to document ongoing toxicities (until resolved to < grade 2) and late toxicities (including second malignancies). For patients who go off protocol treatment with CR, PR, or SD ongoing, follow-up will be required every 12 weeks until relapse (see Appendix I for investigations to be performed). Death Report will be required for all patients. Due within 2 weeks of knowledge of death (see Appendix IV - Documentation for Study). Timing of Day 1 Assessments: Pre-treatment blood draws and physical exams may be done one working day prior to treatment if necessary, and when treatment is to begin on a Monday, may be done on the previous Friday (maximum 72 hours prior to treatment). In order to ensure that nadir counts are not missed, every effort should be made to do interim blood draws within 24 hours of the day specified in the protocol. If a patient shows an AST or ALT ≥ 3 x ULN together with total bilirubin ≥ 2 x ULN, refer to Appendix III for further instructions on cases of increases in liver biochemistry and evaluation of Hy's Law. These cases should be reported as SAEs if, after evaluation, they meet the criteria for a Hy's law case or if any of the individual liver test parameters fulfill any of the SAE criteria. Note: Labs do not need to be repeated Day 1, Cycle 1. In order to ensure that nadir counts are not missed, every effort should be made to do interim blood draws within 24 hours prior to the day specified in the protocol. Vital signs are to be monitored before, during, and after the infusion of tremelimumab and durvalumab with assessment of vital signs to be collected ≤ 30 minutes prior to start of infusion then every 30 ± 5 minutes during infusion and observation periods. A 1-hour observation period is recommended after the first infusion of tremelimumab, during which time durvalumab may be administered (see Section 7.1.3). A second 1-hour observation period is recommended after the first infusion of durvalumab. If no clinically significant infusion reactions are observed during or after the first cycle of tremelimumab and durvalumab, subsequent infusion observation periods can be at the Investigator's discretion but are recommended to be of 30 minutes, i.e., 30 minutes after tremelimumab infusion, during durvalumab infusion, and for 30 minutes after durvalumab infusion. For patients who receive only durvalumab, the recommended observation period is 30 minutes after infusion. In the event that patient is unable to attend clinic, post-progression follow-up may be by means of telephone contact. Hematology, Coagulation and Biochemistry investigation to be done after objective progression ONLY if there are ongoing hematologic AEs that are related to protocol treatment. If abnormal, T3 and T4 must be measured. To ensure comparability, scans must identify and report each lesion at baseline and at reassessment during treatment. These scans must be performed using identical technique (i.e. scans performed immediately following bolus contrast administration using a standard volume of contrast, the identical contrast agent, and preferably the same scanner). Tumour evaluations must be consistently performed every 8 weeks (i.e. at 8 weeks, 16 weeks, 24 weeks, 32 weeks etc. from randomization) until objective disease progression is documented (as described in Section 8). Sites should adhere to this calendar-based schedule regardless of any delays in treatment. If a radiology scan is done off schedule, future protocol-required scans should still be performed based on the original schedule, i.e. every 8 weeks counting from randomization (not from the date of the off schedule scan). For women of childbearing potential only. May be urine or serum. Pregnancy test (in women of childbearing potential), as part of Pre-Study Evaluation, may include an ultrasound to rule-out pregnancy. See Section 12.0 and the CO.26 Correlative Studies Laboratory Manual for details. Whole blood, plasma and serum should be obtained as close to the time of objective progression as possible and should be done within 28 days (e.g. at the next clinic visit). Blood for correlatives done within 28 days PRIOR to date of progression does not need to be repeated. Adverse Events to be evaluated using the NCI Common Terminology Criteria for Adverse Events (CTCAE v4.0) (see Appendix V). See Section 7 and Appendix III for additional monitoring of patients with toxicity. Follow every adverse event felt related to study therapy until resolved to ≤ grade 2 – i.e. follow-up every 12 weeks until deterioration to ECOG PS 4 and/or end of life care or until all toxicities thought to be possibly-, probably-, or definitely-related to durvalumab or tremelimumab have resolved, returned to baseline, or been deemed irreversible, whichever is longer. To be completed by patient in clinic. | | | | | | |

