9.1.1 Durvalumab +/- Tremelimumab Adverse Events of Special Interest

An adverse event of special interest (AESI) is one of scientific and medical interest specific to understanding of the Investigational Product and may require close monitoring. An AESI may be serious or non-serious.

AESIs for durvalumab ± tremelimumab include, but are not limited to events with a potential inflammatory or immune-mediated mechanism and which may require more frequent monitoring and/or interventions such as steroids, immunosuppressants and/or hormone replacement therapy. **These AESIs may require close monitoring in the treatment arms with durvalumab ± tremelimumab.**

An immune-mediated adverse event (imAE) is defined as an AESI that is associated with drug exposure and is consistent with an immune-mediated mechanism of action and where there is no clear alternate etiology. Serologic, immunologic, and histologic (biopsy) data, as appropriate, should be used to support an imAE diagnosis. Appropriate efforts should be made to rule out neoplastic, infectious, metabolic, toxin, or other etiologic causes of the imAE.

If the Investigator has any questions in regards to an event being an imAE, the Investigator should promptly contact the CCTG.

AESIs observed with durvalumab ± tremelimumab include:

- Diarrhea / Colitis, and intestinal perforation;
- Pneumonitis / Interstitial Lung Disease (ILD);
- ALT/AST increases / hepatitis / hepatotoxicity;
- Neuropathy / neuromuscular toxicities (e.g. Guillain-Barré syndrome, and myasthenia gravis);
- Endocrinopathies (i.e. events of hypophysitis, hypopituitarism, adrenal insufficiency, diabetes insipidus, hyper- and hypothyroidism and type I diabetes mellitus);
- Rash / Dermatitis;
- Nephritis / Blood creatinine increases;
- Pancreatitis (or labs suggestive of pancreatitis - increased serum lipase , increased serum amylase);
- Myocarditis;
- Myositis/polymyositis
- Other inflammatory responses that are rare with a potential immune-mediated aetiology include, but are not limited to, pericarditis, sarcoidosis, uveitis and other events involving the eye, skin, hematological and rheumatological events.

In addition, infusion-related reactions and hypersensitivity/anaphylactic reactions with a different underlying pharmacological etiology are also considered AESIs.

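### Arm 2 laboratory tests after progression are scheduled only for related hematologic events, although every related event must be followed at the same visits

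*Protocol*

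**What the plan says.** All of the following is in the Arm 2 flowsheet, Protocol section 5.2, unless stated otherwise. Footnote numbers follow the order of the list under the table.

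- **Laboratory rows.** The biochemistry row, which includes bilirubin, AST, ALT, creatinine, TSH, amylase and lipase, ends "Serum CEA | X | X ² | X | X | X | X ⁵". The last cell is the 12-weekly visit after progression and carries footnote 5. The cell before it, the 4-week post-treatment visit, is a plain X. Hematology and coagulation have the same pattern.
- **Footnote 5.** The three panels are done after objective progression "ONLY if there are ongoing hematologic AEs that are related to protocol treatment".
- **Adverse event row.** It reads "To be evaluated continuously for adverse events) | X | X ¹³ | X ¹ | X ¹³", so the 12-weekly cell after progression carries footnote 13.
- **Footnote 13.** It opens "Follow every adverse event felt related to study therapy until resolved to ≤ grade 2". It then explains this as "follow-up every 12 weeks until deterioration to ECOG PS 4 and/or end of life care", or until toxicities at least possibly related to either drug "have resolved, returned to baseline, or been deemed irreversible, whichever is longer".
- **Footnote 1.** Patients who leave treatment with unequivocal progression need no continued follow-up after the 4-week visit "except to document ongoing toxicities (until resolved to < grade 2") and late toxicities.
- **Section 9.1.1.** The events of special interest include "ALT/AST increases / hepatitis / hepatotoxicity", creatinine increases, endocrinopathies, and raised lipase or amylase.

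**The concern.** Footnotes 5 and 13 apply to the same visit and do not fit together. The site must follow every related event, but the flowsheet schedules blood work only when the event is hematologic. Several toxicities that the protocol expects from these drugs are detected and graded by chemistry, not by blood count. For these, the visit has no scheduled test to show whether the event has resolved, persisted or worsened.

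The condition also works the wrong way round. A cytopenia brings in ALT, TSH and lipase, which it does not need, while hepatitis brings in no ALT. The protocol gives no reason for this.

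The second problem is when follow-up ends. Footnote 13 states one limit and then explains it as a different one, and footnote 1 gives a third. Two sites could stop at different points and both claim compliance. Toxicity and safety of the combination is a secondary objective (Protocol section 1.2), so that is where any effect would fall.

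**Working it through.** The plan states no figure to reproduce. The check sets the rules side by side.

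**1. What each event schedules at a 12-weekly visit after progression** (no other related hematologic event present)

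| Ongoing related event | Follow-up required (footnote 13) | Biochemistry scheduled (footnote 5) |
|---|---|---|
| Cytopenia | Yes | Yes, the whole row |
| Hepatitis, raised ALT/AST | Yes | No |
| Raised creatinine | Yes | No |
| Thyroid dysfunction | Yes | No |
| Raised amylase or lipase | Yes | No |

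**2. How this reaches the analysis.** Protocol section 9.1.2 does not record abnormalities in protocol-specified tests as adverse events; they are derived from the values submitted. SAP section 7.7.2 uses all values reported after baseline, and the overall hematology and chemistry tables (Tables 48 and 50) show the worst grade per patient. If w is the worst grade already recorded and g the grade of a later value that was not taken, the true entry is max(w, g) and the recorded entry is w. They differ only if g > w.

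- Worst grade 3 on treatment, later grade 1 not measured: max(3, 1) = 3, so the entry is unchanged.
- Worst grade 2, later rise to grade 3 not measured: max(2, 3) = 3, so the table shows 2 and is wrong by one grade.

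**3. When follow-up ends.** Assume the event is above baseline and not irreversible, the patient has not reached ECOG PS 4 or end-of-life care, and *resolved* in footnote 13's later clause means complete resolution.

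| Current grade | Footnote 13, opening (≤ 2) | Footnote 13, later clause | Footnote 1 (< 2) |
|---|---|---|---|
| 1 | Stop | Follow | Stop |
| 2 | Stop | Follow | Follow |
| 3 | Follow | Follow | Follow |
| 4 | Follow | Follow | Follow |

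Footnote 13's two halves disagree at grades 1 and 2. Footnote 1 disagrees with the later clause only at grade 1, and with the opening only at grade 2. Appendix III grades ALT above ULN and up to 3.0 x ULN as 1, and above 3.0 and up to 5.0 x ULN as 2. With a normal baseline, a related ALT of 2 x ULN is therefore released by footnote 1 and kept by the later clause. A related ALT of 4 x ULN is released by the opening words and kept by the other two rules.

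Footnote 13's closing words add another difficulty. Taking the longer of the two limits literally means 12-weekly follow-up to ECOG PS 4 or end-of-life care even after the event has resolved.

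**4. Who is affected.** An Arm 2 patient (120 planned, SAP section 2.1) must be permanently off drug, have progressed, be alive beyond the 4-week visit, and have an ongoing related event detected by laboratory test that is not hematologic. The documents give no rate for this combination, so no count can be derived.

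**The case against.** The strongest reply is that reduced testing after progression is deliberate. Footnote 1 drops most follow-up, footnote 4 allows telephone contact, and physical examination and concomitant medications are blank in the same column. Footnote 5 sets scheduled tests and does not forbid clinically indicated ones. Appendix III asks for frequent liver tests, serial creatinine, and TSH with free T3 and free T4 where an endocrinopathy is suspected, with no limit to the treatment period. Section 9.1 still requires expedited reporting of late related serious events and of immune-related events that need high-dose steroids.

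Most of this stands, and it limits the consequence. It does not explain why biochemistry should depend on a hematologic event. The flowsheet's pointer to Appendix III (footnote 12) sits only on the during-treatment cell. The steroid reporting route does not by itself reach isolated hypothyroidism or modest asymptomatic amylase or lipase elevation, which Appendix III manages without steroids, and reporting is in any case not monitoring.

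On footnote 13, one can read the explanatory clause as giving *resolved* the meaning just stated, grade 2 or lower. That is a fair reading and removes most of the internal conflict. The mismatch with footnote 1 at grade 2 remains, as does the problem with the longer-of-two-limits wording.

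A reader might infer that hepatic or endocrine toxicity goes unmonitored after progression, or that the safety comparison is materially biased. The documents support neither. Needed tests remain available through Appendix III, and an event that is already ongoing has normally contributed its grade to the worst-grade tables. Footnote 5 also appears on the row headings, so one might infer that the 4-week visit loses its tests too, but that cell is a plain X.

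**Conclusion.** The point holds as a wording error in a safety schedule. At the 12-weekly visits after progression in Arm 2, a related hepatic, renal, thyroid or pancreatic-enzyme event must be followed but has no scheduled test. The rules for ending that follow-up are also inconsistent.

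The size is small. The number of patients is unknown and probably low, given the conditions that must coincide. The worst-grade tables change only if an unmeasured later value exceeds the earlier worst grade. Overall survival, alpha and sample size are unaffected.

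The conclusion on scheduling rests on the flowsheet cells as printed. The conclusion on stopping rules at grade 1 also depends on reading *resolved* as complete resolution. The conflict between footnote 13's opening words and footnote 1 at grade 2 does not depend on that reading. The correction is worth making because it is cheap, not because the trial's conclusions depend on it.

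**What to change.** **Footnote 5.** Replace the hematologic condition so that the panels are done after progression only for *ongoing AEs related to protocol treatment that require laboratory monitoring (relevant tests only)*. Limiting it to relevant tests also spares a patient with a cytopenia the unrelated chemistry.

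**Footnotes 1 and 13.** Use one stopping rule in both, for example: *follow each related AE every 12 weeks until it is resolved to < grade 2, returned to baseline or deemed irreversible, or until ECOG PS 4 or end-of-life care, whichever comes first*. Delete the ≤ grade 2 limit and the longer-of-two-limits wording from footnote 13. Simply pointing footnote 1 to footnote 13 as it stands would be worse, because read literally it would extend follow-up of resolved events to ECOG PS 4 or end-of-life care.

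**Cost.** Three footnotes change, with no change to the SAP analyses.

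- A few extra blood draws are needed, including for patients otherwise followed by telephone.
- Under the single rule, persistent related grade 1 events are released, as footnote 1 already does, and are not followed to full resolution.
- Arm 1 has no laboratory tests scheduled after progression (section 5.1), while SAP section 7.7.2 counts all values reported after baseline and Tables 48 and 50 set the arms side by side. The change slightly widens ascertainment in Arm 2 relative to Arm 1, and this should be noted when those tables are read.
- Accrual closed on June 29, 2017 (SAP section 2.1), so the change reaches only patients still in follow-up.

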
5.3 Follow-up for Ineligible Patients

The follow-up requirements for ineligible patients:

- Randomized to **Arm 1** (BSC) include submission of the Baseline Report plus annual follow-up using the Minimal Follow-up Report.
- Randomized to **Arm 2** (tremelimumab and durvalumab) but who have received no protocol therapy include submission of the Baseline Report plus annual follow-up using the Minimal Follow-up Report. Data submission for ineligible participants who have received at least one dose of protocol therapy should be followed according to the protocol to allow for treatment and adverse event assessment.

Note: The dates of objective progression and death must be reported for ineligible patients.

6.0 ENTRY/RANDOMIZATION PROCEDURES

6.1 Entry Procedures

All registration/randomizations will be done through the CCTG web-based, password-protected Electronic Data Capture (EDC) system. Complete details regarding obtaining a password, accessing the system and registering/randomizing patients will be provided at the time of study activation and will also be included in the “EDC Data Management Guidebook”, posted on the CO.26 trial specific website. If sites experience difficulties accessing the system and/or registering/randomizing patients please contact the help desk (link in EDC) or the CO.26 Study Coordinator.

All eligible patients enrolled on the study by each participating centre will be assigned a serial number which must be used on all documentation and correspondence with CCTG.

The following information will be required:

- trial code (CCTG CO.26)
- investigator CCTG user ID
- patient's initials (may be coded)
- informed consent version date, date signed by patient, name of person conducting consent discussion and date signed
- tissue banking consent version date
- confirmation of the requirements listed in Section 4.0, including dates of essential tests and actual laboratory values
- stratification factors

6.2 Stratification

Subjects will be stratified by:

- ECOG Performance Status: 0 vs 1
- Site of tumour:
 - right colon (caecum, ascending colon, hepatic flexure) vs
 - transverse colon vs
 - left colon (within the splenic flexure, descending colon, sigmoid colon, or rectosigmoid junction) vs
 - rectum vs
 - unknown

6.3 Randomization

Randomization will be provided electronically.

Note: The validity of results of the trial depends on the authenticity of and the follow-up of all patients entered into the trial. Under no circumstances, therefore, may an allocated patient's data be withdrawn prior to final analysis, unless the patient withdraws from the trial and requests that data collection/submission cease from the point in time of withdrawal.

All eligible patients admitted to the trial will be followed by the coordinating centre. It is the responsibility of the treating physician to satisfy himself or herself that the patient is indeed eligible before requesting registration/randomization.

All randomized patients are to be followed until death or until sites are informed by CCTG that further follow-up is no longer required. The follow-up requirements for ineligible patients are outlined in Section 4.2.

